approx. = approximately EC = endometrial carcinoma; HNSCC = squamous cell carcinoma of head and neck; Mel = melanoma (excluding uveal); MTD = maximum tolerated dose; NSCLC = non-small cell lung cancer; ORR = objective response rate; RCC = renal cell carcinoma (predominantly clear cell), UC = urothelial carcinoma;

- a: Based on the efficacy and safety results from the first 10 subjects in each cohort, an additional 10 subjects may be enrolled for a total of 20 subjects in each cohort.
- b: The endometrial and renal cell carcinoma cohorts may be expanded to approximately 120 and 145 evaluable subjects, respectively.
- c: This RCC subset includes previously treated subjects who have received 1 or 2 prior therapies and have progressed on treatment with an anti-programmed cell death protein 1 (PD)-1/ PD-1 ligand 1 (PD-L1) mAb.

Once they complete the Treatment Phase, each subject still receiving study treatment will transition into the Extension Phase. Tumor assessments will continue during the Treatment Period of the Extension Phase. As of Amendment 09, subjects in the treatment period of the extension phase who discontinue pembrolizumab for any reason and remain on lenvatinib study treatment will transition to lenvatinib commercial supply if local country regulations permit. As of Amendment 09, tumor assessments will continue during the Extension Phase as per the local standard of care but not less frequent than every 6 months. Tumor assessments will not be performed or collected during the Follow-Up period of the Extension Phase. Subjects who undergo the Off-Tx visit will undergo safety follow-up for AEs for 30 days from the last dose of study treatment. Serious adverse event (SAEs) will be collected for 90 days after the last dose or 30 days following the last dose if the subject initiates new anticancer therapy, whichever is earlier. Transition to commercial lenvatinib will be considered new anticancer therapy. After the end of the safety follow-up period, no data will be collected subsequently. The data cutoff for each Phase 2 cohort will occur when the evaluable subjects in that cohort complete 8 cycles of treatment or discontinue early.

The study will be conducted in 3 phases: a Pretreatment Phase, a Treatment Phase, and an Extension Phase.

The definition of the end of the study for each cohort is the time of data cutoff for the final analysis or the time of last subject/last treatment, whichever occurs later.

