At the end of the study, the sponsor should notify the IRB/IEC and Competent Authority (CA) within 90 days. The definition for end of the study for each cohort is the time of data cutoff for the final analysis or the time of last subject/last treatment, whichever occurs later. It is estimated that the study duration will be 24 months. The sponsor should also provide the IRB/IEC with a summary of the study's outcome.

In the case of early termination/temporary halt of the study, the investigator should notify the IRB/IEC and CA within 15 calendar days, and a detailed written explanation of the reasons for the termination/halt should be given.

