9.1.3.2 Follow-Up Period

As of Amendment 9, the Follow-Up Period will consist of the Off-Tx Visit. No further visits will be conducted. The sponsor has decided to terminate survival follow-up for all subjects currently in survival follow-up.

Survival follow-up data will no longer be collected after the Off-Tx Visit and after 30 days from the last dose of study drugs.

The Follow-up Period consists of the Off-Tx Visit and the Follow-up Visits.

- The Off-Tx Visit will occur within 30 days after the last dose of study treatment. It applies to the Phase 1b subjects who discontinued study treatment early, before completing Cycle 1, and to the Phase 2 subjects who discontinued study treatment early, before completing 8 cycles. Following the completion of the Off-Tx Visit, subjects will transition to the Follow-up Period of the Extension Phase.
- In the Follow-up Period, subjects will be treated by the investigator according to the prevailing local standard of care. Subjects will be followed every 12 weeks (± 1 week) for survival, with tumor assessments performed as detailed in the Schedule of Procedures/Assessments, and subsequent anticancer treatments. Follow-up Visits continue as long as the study subject is alive unless the subject withdraws consent or until the sponsor terminates the study. The sponsor may decide to terminate survival follow-up anytime during the Extension Phase or when all subjects have discontinued study treatment.

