9.5.4.1 Reporting of Serious Adverse Events

All SERIOUS ADVERSE EVENTS, regardless of their relationship to study treatment, must be reported on a completed SAE form by email or fax as soon as possible but no later than 24 hours from the date the investigator becomes aware of the event.

Deaths and life-threatening events should be reported immediately by telephone. The immediate report should be followed up within 24 hours by emailing or faxing the completed SAE form.

Serious adverse events, regardless of causality assessment, must be collected through 90 days after the subject's last dose, or 30 days following the last dose if the subject initiates new anticancer therapy, whichever is earlier. All SAEs must be followed to resolution or, if resolution is unlikely, to stabilization. Any SAE judged by the investigator to be related to the study treatment or any protocol-required procedure should be reported to the sponsor regardless of the length of time that has passed since study completion.

The detailed contact information for reporting of SAEs is provided in the Investigator Study File.

For urgent safety issues, please ensure all appropriate medical care is administered to the subject and contact the appropriate study team member listed in the Investigator Study File.

It is very important that the SAE report form be filled out as completely as possible at the time of the initial report. This includes the investigator's assessment of causality.

Any follow-up information received on SAEs should be forwarded within 24 hours of its receipt. If the follow-up information changes the investigator's assessment of causality, this should also be noted on the follow-up SAE form.

Preliminary SAE reports should be followed as soon as possible by detailed descriptions including copies of hospital case reports, autopsy reports, and other documents requested by the sponsor.

The investigator must notify his/her IRB/IEC of the occurrence of the SAE in writing, if required by their institution. A copy of this communication must be forwarded to the sponsor to be filed in the sponsor's Trial Master File.

Eisai will provide a Safety Reporting Plan (SRP) for lenvatinib and pembrolizumab. The plan will address the following:

- Holder of the Global Safety Database
- Procedures and timelines for the processing of SAEs
- The distribution of expedited SAE reports
- Responsibility for submission to Health Authorities and notifications to investigators and the EC/IRB

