9.5.4.2 Reporting of Pregnancy and Exposure to Study Drug Through Breastfeeding

Any pregnancy in which the estimated date of conception is either before the last visit or within 120 days of the last study treatment or 30 days following last study treatment if the subject initiates new anticancer therapy, whichever is earlier, must be reported. Also, any exposure to study drug through breastfeeding during study treatment or within 120 days of the last study treatment, or 30 days following the last study treatment if the subject initiates a new anticancer therapy, whichever is earlier, must be reported.

If an adverse outcome of a pregnancy is suspected to be related to study drug exposure, this should be reported regardless of the length of time that has passed since the exposure to study treatment.

A congenital anomaly, death during perinatal period, an induced abortion, or a spontaneous abortion are considered to be an SAE and should be reported in the same time frame and in the same format as all other SAEs (see Reporting of Serious Adverse Events [[Section 9.5.4.1](#)]).

Pregnancies or exposure to study drug through breastfeeding must be reported by fax or email as soon as possible but no later than 24 hours from the date the investigator becomes aware of the pregnancy. The contact information for the reporting of pregnancies and exposure to study drug through breastfeeding is provided in the Investigator Study File. The Pregnancy Report Form must be used for reporting. All pregnancies must be followed to outcome. The outcome of the pregnancy must be reported as soon as possible but no later than 24 hours from the date the investigator becomes aware of the outcome.

A subject who becomes pregnant must be withdrawn from the study

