5.6.3 Deaths, Serious and Other Significant Adverse Events

The adverse event verbatim descriptions (investigator terms from the eCRF) will be classified into standardized medical terminology using the Medical Dictionary for Regulatory Activities

(MedDRA) version 19.0 or later. Adverse events will be coded to primary System Organ Class (SOC) and preferred term (PT) using MedDRA.

A treatment-emergent adverse event (TEAE) is defined as an adverse event that had an onset date, or a worsening in severity from baseline (pre-treatment), on or after the first dose of study drug up to the last visit, or 30 days following the last dose of study drug. In addition, if an AE reemerges during treatment, having been present at pretreatment (Baseline) but stopped before treatment, it is also counted as a TEAE. Due to the use of pembrolizumab, serious adverse events (SAEs) occurring up to 90 days after the last dose of study drug will be considered as treatment-emergent serious adverse events.

Only those AEs that are treatment emergent will be included in summary tables. All AEs, treatment emergent or otherwise, will be presented in subject data listings. Treatment-emergent AEs (TEAEs) will be summarized.

The incidence of TEAEs will be reported as the number (percent) of subjects with TEAEs within SOC and PT. Subjects will be counted only once within a SOC and PT. If the subject experienced more than one TEAE within a specific SOC and PT, the subject will be counted with the worst grade for that AE. The number (percent) of subjects with TEAEs will also be summarized by highest Common Terminology Criteria for Adverse Events (CTCAE) grade. In summary, the following TEAE tables will be provided:

- Overview of TEAEs.
- TEAEs by SOC, PT, and CTCAE grade.
- TEAEs with CTCAE grade ≥ 3
- TEAE with outcome of death.
- Treatment-related TEAEs by SOC, PT, and CTCAE grade
- Treatment-related TEAEs with CTCAE grade ≥ 3
- Treatment-related TEAEs with outcome of death

The following subject AE listings (regardless treatment emergent or not) will be provided:

- All adverse events.

A subject data listing of all deaths will be provided with the information of primary reasons of deaths, deaths within 30 days of last dose, deaths > 30 days of last dose, and treatment-related deaths.

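### After Amendment 09 nothing is scheduled between the Off-Tx visit and Day 90 to pick up late SAEs, and the data stop in Protocol 9.1 conflicts with the SAE and pregnancy rules in 9.5.4

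*Protocol*

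**What the plan says.** **Contact after treatment.** Protocol 9.1.3.2 states: "As of Amendment 9, the Follow-Up Period will consist of the Off-Tx Visit. No further visits will be conducted". On timing, the same section says: "The Off-Tx Visit will occur within 30 days after the last dose of study treatment". The older text on 12-weekly visits still stands below this, but the Amendment 09 statement overrides it and is repeated in 9.3.3 and in footnotes v and bb to Tables 8 and 9. Survival follow-up stops as well.

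**Safety windows.** Protocol 9.1 and 9.5.1.5.1 collect AEs for 30 days after the last dose. Those two sections and 9.5.4.1 collect SAEs for 90 days, cut to 30 days if new anticancer therapy is started. Section 9.1 counts a switch to commercial lenvatinib as such therapy. SAP 5.6.3 uses the 90-day limit in the analysis: "serious adverse events (SAEs) occurring up to 90 days after the last dose of study drug will be considered as treatment-emergent".

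**Stop of data collection.** At the end of the same paragraph of 9.1, after the windows are set: "After the end of the safety follow-up period, no data will be collected subsequently".

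**Duties without that limit.** Protocol 9.5.4.1 requires: "All SAEs must be followed to resolution or, if resolution is unlikely, to stabilization". Sections 9.5.1.5.1 and 9.5.1.5.2 say the same. Section 9.5.4.1 also wants SAEs related to treatment or to a protocol procedure reported however long after study completion. Section 9.5.4.2 covers pregnancies conceived "within 120 days of the last study treatment" (30 days with new anticancer therapy) and has every pregnancy followed to its outcome.

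**The concern.** There are two separate problems.

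First, the analysis relies on a 90-day SAE window, but the schedule supports at most its first 30 days. After the Off-Tx visit, a site learns of a serious event only if the subject or another physician volunteers it. Protocol 9.4.1.2 itself warns that events of possible immune origin can arise months after pembrolizumab has been stopped. An SAE rate that looks complete to Day 90 may therefore be incomplete after the Off-Tx visit.

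Second, a site that takes the closing sentence of 9.1 literally would stop recording an unresolved SAE, a late related SAE or a pregnancy conceived after Day 90. Sections 9.5.4.1 and 9.5.4.2 require each of these. No cross-reference in 9.1 tells the site which rule prevails.

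**Working it through.** The plan gives no figure to reproduce. The check compares the stated windows, counting days from the last dose.

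| Item | Days | Source |
|---|---|---|
| Off-Tx visit, the only scheduled contact | 0 to 30 | Protocol 9.1.3.2 |
| AE collection | to 30 | 9.1, 9.5.1.5.1 |
| SAE collection, no new anticancer therapy | to 90 | 9.1, 9.5.1.5.1, 9.5.4.1 |
| SAE collection, new anticancer therapy | to 30 | same sections |
| Treatment-emergent SAE in the analysis | to 90 | SAP 5.6.3 |
| Pregnancy (conception), no new anticancer therapy | to 120 | 9.5.4.2 |
| SAE follow-up; related SAEs; pregnancy outcome | no day limit | 9.5.4.1, 9.5.4.2 |

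**1. SAE window without scheduled contact.** With the Off-Tx visit on Day *t* (0 ≤ *t* ≤ 30), the gap is 90 − *t* days.
- Latest visit: 90 − 30 = 60 days, and 60/90 = 67% of the window.
- Earliest visit: 90 − 0 = 90 days.

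If *t* is below 30, the last 30 − *t* days of the AE window are also without contact.

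**2. Does another provision fill the gap?** The only telephone contact in Tables 8 and 9 is around Day 8 of Cycle 1 (footnote h). Section 9.5.5 provides for contact by mail or phone, but for subjects who have stopped coming to visits, and here no visit is due. The AEs/SAEs row in both tables is marked as running throughout. Its column span is not legible in the text available, so nothing here rests on it.

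**3. Subjects to whom the gap applies.** Where new anticancer therapy is started, including commercial lenvatinib, the SAE window is 30 days and there is no 60-day gap. The point concerns the remaining subjects, whose number the documents do not give. Footnote v ties the recording of later anticancer therapy to survival follow-up, which has now ended. A site may therefore not know which window applies unless it asks.

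**4. Data stop against the pregnancy window.** Taking Day 90 as the end of safety follow-up (the longest window in that paragraph of 9.1), 120 − 90 = 30 days of the pregnancy window fall after the stop. That is 30/120 = 25%.

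**5. Data stop against SAE follow-up.** An SAE that starts on Day 85 and is still open on Day 91 must be followed under 9.5.4.1, yet 9.1 says nothing more is collected. No arithmetic is needed: the two sentences cannot both be obeyed.

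**6. Would the dropped 12-weekly visit have covered Day 90?** Counting 84 ± 7 days from the Off-Tx visit (an assumption), the first visit fell between 0 + 84 − 7 = Day 77 and 30 + 84 + 7 = Day 121. It fell by Day 90 at its nominal date only if *t* ≤ 90 − 84 = 6, and at the early edge of its window only if *t* ≤ 90 − 77 = 13. After an Off-Tx visit on Day 30 it fell on Days 107 to 121.

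**The case against.** The best reply is that the protocol still demands what matters. Section 9.1 keeps SAE collection to Day 90 in the same paragraph as the disputed sentence, so safety follow-up naturally includes Day 90. Sections 9.5.4.1 and 9.5.4.2 are specific mandatory rules and would prevail over a general design sentence. How a site finds SAEs is then a matter of method. Much of this stands, and it rules out several stronger readings.

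- A reader might infer that Amendment 09 ends all contact and that SAEs to Day 90 are lost. It ends visits and survival follow-up, while the reporting duties remain. Under-ascertainment is a risk, not a stated loss.
- A reader might infer that the study ends at last treatment, so the windows close with it. The definition in 5.1 takes the later of the final-analysis cutoff and "the time of last subject/last treatment, whichever occurs later". It dates from Amendment 04, and 9.5.4.1 carries related-SAE reporting past study completion. Redefining end of study would be a preference.
- A reader might infer that SAE rates are not comparable with those of earlier subjects. The dropped visits were for survival and later anticancer therapy, and step 6 shows that the first could fall after Day 90.
- A reader might want a percentage undercount. That needs the number of subjects still on treatment at Amendment 09, the share without new therapy, the share of SAEs starting after the Off-Tx visit, and the completeness of unprompted reports. The documents give none of these.

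The reply does not supply a scheduled contact after the Off-Tx visit or an exception in the 9.1 sentence. Those two gaps remain.

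**Conclusion.** The concern holds in limited form. For subjects without new anticancer therapy, at least 60 of the 90 SAE-window days (67%) have no scheduled contact, and up to 90 if the Off-Tx visit is held on the day of the last dose. Late treatment-emergent SAEs may be under-ascertained by an unknown amount. Independently, the data-stop sentence in 9.1 contradicts the SAE and pregnancy rules in 9.5.1.5.1, 9.5.1.5.2, 9.5.4.1 and 9.5.4.2. This includes a 30-day overlap with the pregnancy window if safety follow-up is taken to end at Day 90.

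The point bears on the completeness of safety data from subjects stopping treatment after Amendment 09. It does not touch the primary endpoint, response as of Week 24. It is worth correcting because the correction is cheap, not because a bias of known size has been shown.

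**What to change.** 1. **Protocol 9.1:** add an exception to the data-stop sentence, for example: *except follow-up of SAEs to resolution or stabilization, related SAEs, and pregnancies, as in 9.5.4*.
2. **Protocol 9.1.3.2 and Tables 8 and 9:** add one documented telephone SAE check at the close of the existing 90-day window for subjects who have not started new anticancer therapy. The site should first ask whether such therapy has begun, since that decides which window applies.
3. **Same places:** add an AE check at Day 30 where the Off-Tx visit was held earlier.

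The 30-, 90- and 120-day windows and the end-of-study definition stay as they are. The cost is amendment wording and one or two short calls per subject still on treatment. SAP 5.6.3 needs no change for this purpose.

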9.1.1 Pretreatment Phase

The Prerandomization Phase will last for 28 days and will include a Screening Period and a Baseline Period.

9.1.1.1 Screening Period

Screening will occur between Day -28 and Day -3. The purpose of the Screening Period is to obtain informed consent and to establish protocol eligibility. Informed consent will be obtained after the study has been fully explained to each subject and before the conduct of any screening procedures or assessments. Procedures to be followed when obtaining informed consent are detailed in [Section 5.3](#). Tumor assessments performed up to 28 days prior to dosing are acceptable as screening tumor assessments if they are consistent with the requirements for this protocol.

The Screening Disposition case report form (CRF) page must be completed to indicate whether the subject is eligible to participate in the study and to provide reasons for screen failure, if applicable.

9.1.1.2 Baseline Period

The purpose of the Baseline Period is to confirm protocol eligibility as specified in the inclusion/exclusion criteria. Baseline assessments may be performed from Day -3 to Day -1 or on C (C) 1 D1 prior to dosing.

Subjects who complete the Baseline Period and meet the criteria for inclusion/exclusion ([Sections 9.3.1](#) and [9.3.2](#)) will begin the Treatment Phase.

9.1.2 Treatment Phase

The Treatment Phase will begin with the administration of the first dose of study treatment to the first subject in Cycle 1 and continues in 21-day (3-week) cycles. The Phase 1b and Phase 2 Treatment Periods are described below:

9.1.2.1 Treatment Period

- **Phase 1b:** The Treatment Period for each subject ends after they complete Cycle 1 of treatment or they discontinue early. Those that discontinue study treatment in Cycle 1 transition to the Off Treatment (Off-Tx) Visit of the Follow-up Period of the Extension Phase. Those that complete Cycle 1 transition to the Treatment Period of the Extension Phase.
- **Phase 2:** The Treatment Period for each subject ends after they complete 8 cycles of treatment unless they discontinue early. Those that discontinue study treatment before completing 8 cycles transition to the Off-Tx Visit of the Follow-up Period of the Extension Phase. Those that complete 8 cycles transition to the Treatment Period of the Extension Phase.

9.1.3 Extension Phase

The Extension Phase consists of 2 periods, the Treatment Period and the Follow-up Period.

9.1.3.1 Treatment Period

Subjects still receiving study treatment at the end of the Treatment Phase will continue to receive the same study treatment in the Treatment Period of the Extension Phase. Those subjects that discontinue study treatment transition to the Off-Tx Visit of the Follow-up Period of the Extension Phase. Note that all AEs must be captured for 30 days after last dose of study medication.

9.1.3.2 Follow-Up Period

As of Amendment 9, the Follow-Up Period will consist of the Off-Tx Visit. No further visits will be conducted. The sponsor has decided to terminate survival follow-up for all subjects currently in survival follow-up.

Survival follow-up data will no longer be collected after the Off-Tx Visit and after 30 days from the last dose of study drugs.

The Follow-up Period consists of the Off-Tx Visit and the Follow-up Visits.

- The Off-Tx Visit will occur within 30 days after the last dose of study treatment. It applies to the Phase 1b subjects who discontinued study treatment early, before completing Cycle 1, and to the Phase 2 subjects who discontinued study treatment early, before completing 8 cycles. Following the completion of the Off-Tx Visit, subjects will transition to the Follow-up Period of the Extension Phase.
- In the Follow-up Period, subjects will be treated by the investigator according to the prevailing local standard of care. Subjects will be followed every 12 weeks (± 1 week) for survival, with tumor assessments performed as detailed in the Schedule of Procedures/Assessments, and subsequent anticancer treatments. Follow-up Visits continue as long as the study subject is alive unless the subject withdraws consent or until the sponsor terminates the study. The sponsor may decide to terminate survival follow-up anytime during the Extension Phase or when all subjects have discontinued study treatment.

